9.3 Interim analyses and Stopping Rules

An interim analysis is not planned.

9.4 Data Analyses

We will establish the feasibility of the SNF-PC intervention in persons with ADRD/CI using established benchmarks based on published recommendations for evaluating pilot studies. We will track the number of eligible patients, monitor follow-up, document rates of eligibility, enrollment, and completion of the intervention, and collect the outcome measures with <5% missing data. We will determine clinician fidelity to the SNF-PC protocol

We also will estimate the effect size of the SNF-PC intervention on pre-post changes in the POSv2, SWC-EOLD, and the SM-EOLD relative to the control group. These estimates will be summarized with two-sided 90% Confidence Intervals and p-values corresponding to tests against the null hypothesis of no (zero) difference.

We also will examine the demographics, clinical characteristics, and palliative care needs of people with ADRD/CI versus non ADRD/CI serious illnesses during post-acute SNF care. As the

comparisons will be made using baseline/pre-intervention information, all 50 participants enrolled in this study are potentially includable in the analysis.

The primary analysis will be to compare the mean pre-post changes in the POS v2 between the intervention and control arms. Linear regression models will be used to compare the two groups. The within-arm changes and differences between arms will be summarized with two-sided 90% CIs and p- values corresponding to tests against the null hypothesis of no (zero) change or difference. We will also explore subgroup effects of the intervention on endpoints by testing for statistical interactions between the binary group indicator and covariates of interest such as sex, age, and race.

Other key parameters needed to plan a follow-up study will be estimated as well, including the standard deviation (SD) and intraclass correlation coefficient (ICC) of each endpoint. The ICC summarizes the degree of correlation of values among patients within a site, which is an important parameter when planning a future cluster randomized controlled trial.

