1.2 Secondary Objectives (2)

This study will compare the demographics, clinical characteristics, and palliative (PC) needs of people with ADRD/CI versus non ADRD/CI serious illnesses during post-acute SNF care in NHs.

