3 STUDY DESIGN AND DURATION

3.1 Design

The study team will conduct a two-arm non-randomized controlled pilot clinical trial enrolling 50 persons with ADRD/CI who are in post-acute SNF NH care to meet the study objectives.

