3.2 Enrollment Numbers

We anticipate screening up to 150 participants. Up to 50 patients with ADRD/CI admitted to 11 SNF NHs owned and/or operated by Acts Retirement Life Communities (“Acts”) will be enrolled.

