4 SELECTION AND ENROLLMENT OF PARTICIPANTS

4.1 Key Inclusion Criteria

Patients: **1)** admitted for SNF post-acute care at a participating NHs following a recent hospitalization, **2)** age \geq 60 years old, **3)** speaks English (if verbal), **4)** if non-verbal/unable to participate in a conversation and/or unable to make decisions, has a legally authorized representative (LAR)/surrogate decision maker who can make decisions for the patient as determined by Acts staff, **5)** documented ADRD or CI (BIMS \leq 12) diagnosis in the medical record, **6)** at least one global indicator for PC at SNF admission (provider would not be surprised if patient died within 1 year, believes the patient would benefit from advance care planning or symptom management; frequent hospital or NH SNF admissions; complex care requirements; decline in function; feeding intolerance; unintended decline in weight; or previous hospice assessment or enrollment and subsequent discharge).

Surrogate/LAR: **1)** \geq 18 years old; **2)** family member or friend of an eligible patient as determined by Acts staff; **3)** speaks English

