4.2 Key Exclusion Criteria

Patients: **1)** who have previously received or are referred for PC by their primary care team, **2)** with a discharge plan within 48 hours of screening, **3)** currently receiving hospice care, **4)** who do not have one global indicator of need, **5)** not recently hospitalized, **6)** not diagnosed with ADRD/CI (BIMS \leq 12), **7)** $<$ 60 years of age, **8)** that are non-English speaking, (if verbal) and **9)** if unable to make decisions, do not have an LAR/surrogate decision maker.

Surrogate/LAR: **1)** < 18 years of age, **2)** not a family Member or friend of an eligible patient, **3)** non-English speaking

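### The only secondary objective compares ADRD/CI with non-ADRD/CI patients, but all 50 enrolled patients have ADRD/CI and no non-ADRD/CI data source is named

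*Combined protocol and SAP*

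**What the plan says.** Section 1.2 lists one secondary objective: "This study will compare the demographics, clinical characteristics, and palliative (PC) needs of people with ADRD/CI versus non ADRD/CI serious illnesses". Section 9.4 repeats it as a planned analysis of "palliative care needs of people with ADRD/CI versus non ADRD/CI serious illnesses during post-acute SNF care". Because the comparison uses baseline information, 9.4 adds that "all 50 participants enrolled in this study are potentially includable in the analysis".

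The population is defined in four places:

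- Section 3.1 enrols "50 persons with ADRD/CI who are in post-acute SNF NH care to meet the study objectives".
- Section 3.2 gives the enrolment as "Up to 50 patients with ADRD/CI admitted to 11 SNF NHs".
- Inclusion criterion 5 in 4.1 requires "documented ADRD or CI".
- Exclusion criterion 6 in 4.2 removes patients "not diagnosed with ADRD/CI".

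The control condition in 6.1 is usual care. It is given to patients who meet the same criteria.

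**The concern.** The objective needs two groups that differ on ADRD/CI status, and the design enrols only one of them. Section 3.1 ties the objectives to the 50 enrolled patients, so a reader who follows the plan as written finds no comparator.

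At stake is the whole secondary objective. If an outside cohort is intended, the comparison is external and perhaps non-concurrent. Whether it can be interpreted then depends on who is in that cohort, how large it is and which variables were recorded in the same way. None of this is fixed. A comparator and variable list chosen after the data have been seen would leave room for selective reporting.

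**Working it through.** The plan gives no sample size, power or precision for this comparison. Its only power statement (9.2) concerns the within-intervention-group change in SWC-EOLD. That figure reproduces: noncentrality 2.7 / (4.9 / √22) = 2.7 / 1.045 = 2.58, which gives power 0.804 from the noncentral t with 21 degrees of freedom at two-sided α = 0.1, against the stated 80%. It has no bearing on the secondary objective.

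**Count by ADRD/CI status**

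- Enrolled: 2 arms × 25 (9.2) = 50, matching 3.1 and 3.2.
- Inclusion 5 and exclusion 6 apply to both arms, so ADRD/CI = 50 and non-ADRD/CI = 50 − 50 = 0.
- The variance of a difference in means is σ²(1/50 + 1/m), where m is the comparator size. It is undefined at m = 0, so there is no estimate, interval or test.

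**Search for another source**

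1. *Parent study.* It is mentioned once, in 9.2, to support the assumption that up to 10% of outcomes will be unavailable. Its population, size and measures are not given.
2. *Screening records.* Section 3.2 states "We anticipate screening up to 150 participants", and 4.3 has records reviewed against the inclusion criteria. Nothing describes retaining or analysing data on patients screened out. Section 6.1 abstracts demographics for participants, and the eligibility percentage in objective 1a takes ADRD/CI patients as its denominator.
3. *Baseline surveys.* Sections 6.1 and 6.3 read as though every new admission is surveyed. Section 4.3 is more specific: the instruments follow confirmation of eligibility and a decision to enrol, and non-ADRD/CI patients are ineligible.
4. *REDCap.* The import facility in 10.1 is a general software feature, not a data plan.
5. *Analysis method.* The linear regression in 9.4 is specified for intervention versus control. No method is given for the ADRD/CI contrast.

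**Why the comparator size must be stated (illustration on assumed sizes)**

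The documents give no m. Assuming independent patients and a common SD, the 90% CI half-width for a baseline difference, in SD units, is 1.645 × √(1/50 + 1/m):

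| Assumed m | Calculation | Half-width (SD) |
|---|---|---|
| 25 | 1.645 × √0.06 | 0.40 |
| 50 | 1.645 × √0.04 | 0.33 |
| 100 | 1.645 × √0.03 | 0.28 |

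**The case against.** The strongest reply is that the 50 are only the ADRD/CI side. The sentence in 9.4 on who can be included makes sense on that reading. Section 9.2 shows that a related study is under way, and 5.1 says the intervention was not designed specifically for ADRD/CI, which fits a wider programme. If so, the defect is an unnamed source and one sentence might repair it. This stands as a possibility. It does not supply the source, its size, its eligibility or a method, and 3.1 points to the enrolled patients alone.

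Three stronger readings are tempting, and the documents do not support them.

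- A reader might infer that no comparator exists and the objective is impossible. The text shows only that none is identified. The section numbering also passes over 11.1 and 12, although the sections where a comparator would be defined are present.
- A reader might subtract planned enrolment from planned screening to bound a comparator drawn from screening records. Both figures in 3.2 are upper limits, so the subtraction is not a ceiling: 150 screened with 40 enrolled would leave 110. The number without ADRD/CI is not given.
- A reader might infer that the comparison is largely unworkable because 6.3 calls SWC-EOLD and SM-EOLD specific to ADRD. The objective names no instrument. Demographics come from records, the global indicators do not depend on dementia, and satisfaction is not part of this objective. The label is a reason to list the shared variables, not a measure of harm.

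It is also fair to say that this is a descriptive aim in a 50-patient pilot.

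**Conclusion.** The point holds in this form: the sole secondary objective has no identified non-ADRD/CI group, and from the data described the comparison is 50 versus 0 and cannot be estimated. This is more than missing detail, because the eligibility criteria exclude the patients that the objective needs and 3.1 says the enrolled 50 serve the objectives. It should be fixed before analysis.

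The feasibility objective and the comparison of arms on POSv2, SWC-EOLD and SM-EOLD do not depend on it. The conclusion assumes that inclusion 5 and exclusion 6 are applied as written, that 4.3 governs who receives the baseline instruments, and that no comparator is defined outside the text available.

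**What to change.** Revise 1.2, 3.1 and 9.4 in one of two ways.

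(a) **If a source exists and may be used**

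- Name it and give its n.
- Apply all the trial's patient eligibility criteria other than ADRD/CI status, as far as its data allow: SNF setting, recent hospitalization, age, language, surrogate availability where needed, global indicator, no prior or referred PC, no hospice, and no discharge plan within 48 hours. Report any that cannot be applied.
- List the baseline variables collected the same way in both groups and limit the comparison to these.
- Report differences with 90% CIs.
- State that the comparator is external and, if so, non-concurrent.

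(b) **If no source exists**, replace the comparison with a description of baseline demographics, clinical characteristics and PC needs in the ADRD/CI participants, both arms pooled (n up to 50).

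Under either option, reconcile the wording in 6.1 and 6.3 that has every new admission surveyed with 4.3, which limits the instruments to eligible people who decide to enrol.

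The cost is wording, and no extra patients are enrolled. Option (a) also needs confirmation that the data exist, may be used and contain matching variables, and it relies on an external group whose case mix may differ even after alignment. Option (b) narrows the objective.

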10 DATA COLLECTION AND QUALITY ASSURANCE

10.1 Data Collection/Management

Study data will be entered and managed using REDCap (<http://www.project-redcap.org>) which is a secure, web-based application. The University of Maryland is a member of the REDCap consortium, and this application is freely available to consortium members. REDCap provides: 1) an intuitive interface for data entry (with data validation), 2) audit trails for tracking data entry and changes, 3) automated export procedures for seamless data downloads to common statistical packages, 4) procedures for importing data from external sources, and 5) advanced features, such as branching logic and calculated fields.

10.2 Quality Assurance

10.2.1 Training

To maximize quality control, the study team will be trained in all data collection and entry procedures. A designated study team member will monitor data collection by checking completed data fields.

10.2.2 Metrics

The study team will utilize double-data entry methods on a 10% random sample, with checks for discordant errors, and as data are entered into the REDCap system.

10.2.3 Protocol Deviation

Protocol deviations will be captured, documented, and reviewed by a member of the study team during interaction with Acts staff and/or participants/LARs. The PI will monitor deviations and the team will review each deviation for its root cause and assess whether a modification to the protocol is needed.

11 PARTICIPANT RIGHTS AND CONFIDENTIALITY

Confidentiality will be maintained by adhering to HIPAA guidelines. The study team will keep all data confidential in accordance with state and federal laws. Data will not be linked to

participant identifying name in the study database. Any data, specimens, forms, reports, or audio recordings, and other records that leave the site will be identified only by a participant identification number (Participant ID, PID) and stored in secure computer files and locked filing cabinets to maintain confidentiality. All computer entry and networking programs will be done using PIDs only. Information will not be released without written permission of the participant, except as necessary for monitoring by IRB, the FDA, the NIA, and the OHRP. The study team will destroy the records at the earliest opportunity following data analysis and study completion.

11.2 Ethical Considerations

The guiding ethical principles being followed by the study include the NIH Common Rule.

